## 2. INTRODUCTION

*This is a 12-month open-label, flexible-dose study in pediatric subjects 1 month through 16 years of age with partial-onset seizures (POS), who have participated in Study A0081041 (4-16 years of age) or Study A0081042 (1 month-3 years of age) and pediatric and adult subjects 5-65 years of age with Primary Generalized Tonic-Clonic (PGTC) seizures who have participated in Study A0081105. Subjects who have completed the studies cited above will be eligible for screening for this study. For subjects who have participated in, but did not complete Studies A0081041, A0081042, or A0081105, eligibility for Study A0081106 will be considered on a case by case basis. A minimum of 4 weeks in the double-blind treatment phase of either Study A0081041 or Study A0081105 will be required for consideration of enrollment into Study A0081106.*

*Selected sites that are not participating in studies A0081041 or A0081042 may screen and enroll pediatric subjects (1 month to 16 years of age) with partial onset seizures directly into Study A0081106 provided they meet the study inclusion/exclusion criteria. When subject enrollment for Studies A0081041 and A0081042 is complete, sites that were enrolling subjects in Studies A0081041 or A0081042 may screen and enroll pediatric subjects (1 month to 16 years of age) with partial onset seizures directly into Study A0081106 until enrollment into Study A0081106 is closed by Pfizer.*

[figure not shown]
### 2.1. Study Design

*The day of the last visit (completion of taper phase) of Studies A0081041, A0081042, and A0081105 is designated as Day 1 (Visit 1A) of this study. Baseline values for analysis of change in safety endpoints will be the assessments made prior to initiating double-blind dosing at Visit 1 of Studies A0081041, A0081042, or A0081105. For subjects directly entering Study A0081106 without participation in one of the studies above, baseline values for analysis of change in safety endpoints will be the assessments made at the first visit (Screening Visit 1B) of this study.*

*Subjects will return for the designated assessments of safety, tolerability, and drug accountability at Week 1 (Visit 2), Month 1 (Visit 3), Month 2 (Visit 4), Month 4 (Visit 5), Month 6 (Visit 6), Month 9 (Visit 7), Month 12/Early Termination (Visit 8), and Follow-up (Visit 9). Investigator site staff will contact the subject and/or parent/caregiver by telephone at least monthly between visits, to address questions, assess safety and adverse events, and ensure compliance with study directives.*

*At Visit 2 and subsequent visits thereafter, the investigator or designee will review seizure diary data and tolerability with the subject and may adjust the dose at his/her discretion.*

### Study Design Diagram:

### 2.2. Statistical Power and Sample Size

*This study will enroll a sufficient number of subjects to ensure that 100 pediatric subjects (1 month to 16 years of age) complete one year of adjunctive treatment. Pediatric subjects with partial onset seizures (who have participated in Studies A0081041, A0081042, or directly enrolled into this study) or with PGTC seizures (who have participated in Study A0081105) are included.*

### 2.3. Study Objectives

*To evaluate the long-term safety and tolerability of pregabalin in pediatric subjects 1 month through 16 years of age with partial onset seizures and pediatric and adult subjects 17-65 years of age with PGTC seizures.*

### 3. INTERIM ANALYSES, FINAL ANALYSES AND UNBLINDING

Not applicable. This is an open-label trial.

### 4. HYPOTHESES AND DECISION RULES

#### 4.1. Statistical Hypotheses

Not applicable. No formal statistical analysis will be performed.

#### 4.2. Statistical Decision Rules

Not applicable. No formal statistical analysis will be performed.

## 5. ANALYSIS SETS

### 5.1. Full Analysis Set (Safety Population)

*The primary analysis set will be the Safety population which will include subjects who took at least one dose of the study medication in this study.*

### 5.2. 'Per Protocol' Analysis Set (PP Population)

None. Protocol Deviations will be addressed (See [Section 5.6](#)) but no PP analyses are planned.

### 5.3. Safety Analysis Set

*The primary analysis set for safety will be the Safety population which will include subjects who took at least one dose of the study medication in this study.*

### 5.4. Other Analysis Sets

Not applicable.

### 5.5. Treatment Misallocations

Not applicable.

### 5.6. Protocol Deviations

The list of protocol deviations will be compiled and evaluated for major deviation prior to database closure and the listing will be provided.

## 6. ENDPOINTS AND COVARIATES

### 6.1. Efficacy Endpoint(s)

*All seizure information will be addressed in safety.*

### 6.2. Safety Endpoints

*Safety and tolerability will be evaluated at each study visit. Data on the following endpoints will be collected:*

- Adverse event (AE) data (occurrence, nature, intensity, and relationship to study drug).
- Physical and neurological examinations.
- Vital signs.
- *Growth and development parameters (height and weight) including Tanner stage* (Tanner stage not applicable for subject from study A0081042) for pediatric subjects.
- Clinical laboratory data (hematology, chemistry, urinalysis).

- Electrocardiograms (ECGs).
- 28-day seizure rate (number of seizures per 28-day period).
- Assessment of suicidal ideation and behavior.
- *Cognitive testing* (Only A0081041 subjects who participated in study A0081106 and A0081106 Direct Enrollers).

In addition, identification of subjects meeting the definition of Hy's law will be evaluated.

### 6.2.1. Adverse Events

All AEs will be coded using the MedDRA coding dictionary. All AEs (serious and non-serious) reported from onset of the first day of A0081106 study treatment through and including 999 calendar days after the last administration of the study drug will be considered treatment emergent AEs (TEAEs). For subjects who participated in the previous studies, AEs that were ongoing from their previous study were recorded in A0081106 and were considered treatment-emergent only if the severity worsened.

### 6.2.2. Prior and Concomitant Treatments and Medications

Concomitant medications, defined as medications that are ongoing or started on or after the first day of A0081106 study treatment up to the last dose of study treatment, and prior medications, defined as medications that stopped prior to the first day of study treatment, will be summarized using the WHO-drug coding dictionary. In addition, concomitant and prior non-drug treatments/procedures will be summarized using the MedDRA coding dictionary.

### 6.2.3. Seizure Frequency

The seizure frequency for PGTC and POS seizure will be based on the 28-day seizure rate at each visit and overall (all treatment days during the treatment phase, excluding the taper phase), calculated as follows:

$$\text{28 day seizure rate} = \frac{\text{\# of seizures since last visit}}{[\text{\# of days since last visit} - \text{\# of missing diary days since last visit}]} \times 28$$

- Number of days since last visit is defined as: Date of last diary data entry since last visit – Date of first diary data entry since last visit +1.

Calculations will be made, using A0081106 visit schedule, for Week 1 (Visit 2), Month 1 (Visit 3), Month 2 (Visit 4), Month 4 (Visit 5), Month 6 (Visit 6), Month 9 (Visit 7), Month 12 (Visit 8) and Overall.

The 28-day seizure rate for all POS will be computed for subjects from Studies A0081042, A0081041, and direct enrollers, for each visit in study A0081106 and overall. Since these subjects were all <17 years of age at the time of entry to the previous studies, there will be only one age cohort.

The 28-day seizure rate for PGTC seizures will be computed for subjects from Study A0081105 for each visit in Study A0081106 and overall. The 28-day PGTC seizure rate will also be summarized by age cohort (5 to 16 years and  $\geq 17$  years).

Number and percent of subjects who experienced at least one unclassified epileptic seizure, status epilepticus, myoclonic, absence seizure, tonic/tonic & clonic seizure will be computed for all subjects for each visit in study A0081106 by primary seizure type cohorts (PGTC, POS). These seizure types are not part of the PGTC or POS 28-day seizure rate.

The following specifications in regard to the handling of special cases for the seizure diary are also considered:

1. Any unplanned diary records will be mapped to planned visits by comparing the diary date against the dosing visits and assigned to the first visit that occurs after the unplanned diaries date.
2. If the subject has multiple diary records on the same date, then the below algorithm will be used to select the record for analysis:
  - a. Select 'DONE' records over 'NOT DONE'.
  - b. If one of the repeated records has 'NO Seizures' and the other is with some positive number as result, then select record with positive number of seizures.
  - c. If both/multiple repeated records have positive number of seizure, then include all seizures from both pages.
3. The data is collected in two ways due to CRF amendment. Per earlier version of CRF, the diary data is collected daily. Per the revised CRF, diary start and end dates are collected and the data are entered only when a seizure has occurred. If the data are collected on the revised CRF, then dates collected on CRF are used. Otherwise the minimum/maximum dates per visit from daily collection dates are used.

#### **6.2.4. Suicidal Ideation and Behavior (SIB) Assessments During the Clinical Trial**

*The correct age appropriate scale to assess suicidal ideation and behavior risk was used based on the guidance in the protocol, specifically the use of the Child Behavior Checklist (CBCL) for subjects <6 years of age) and the Columbia-Suicide Severity Rating Scale (C-SSRS) for subjects 6 - 65 years of age.*

C-SSRS responses will be mapped to the Columbia Classification Algorithm of Suicide Assessment (C-CASA). (see [Appendix 2](#)).

The following 3 endpoints are key endpoints for suicidal ideation and behavior data analysis and evaluation:

1. Suicidal Behavior.
2. Suicidal Ideation.

### 3. Suicidal Behavior or Ideation.

**Suicidal behavior:** A subject is said to have suicidal behavior if the subject has experienced any of the following events (C-CASA event codes 1-3, according to the 2010 FDA draft guidance to industry):

1. Completed suicide.
2. Suicide attempt; or
3. Preparatory acts toward imminent suicidal behavior.

**Suicidal ideation:** Any observed suicidal ideation maps to a single C-CASA category. The C-SSRS, for example, includes five ideation questions (that map to C-CASA category 4) with increasing severity.

*There are currently no validated scales to assess suicidal ideation and behavior in children below age 6, and suicidal ideation and behavior is an extremely rare occurrence in this age group. Children in this age group and young school-aged children are more likely to demonstrate aberrant behaviors that place them at-risk for self-injurious behaviors. The CBCL will be used in this trial for children <6 years of age at Screening and follow-up visits to assess for behavioral and emotional issues, including those that may be related to suicidal ideation and behavior. For this trial, scores on the Withdrawn, Internalizing Problems subscales and the Total Problem scales will be examined. Higher scores on the CBCL indicate higher levels of problematic behaviors or dysfunction. The CBCL scoring algorithm allows for a subject's scores to be standardized using scores from a normal population. These standardized scores are referred to as T-scores on the CBCL report. For this study, a cut-off of  $\geq 68$  on the T-scores for the Withdrawn, Internalizing Problems subscales and the Total Problem scales will be used. The CBCL in this study is used for subjects age 4 to <6 years of age.*

#### 6.2.5. Cognitive Testing During the Clinical Trial

The CogState Battery will be completed for pediatric partial onset seizure subjects 4-16 years of age only (subjects from A0081041 and A0081106 Direct Enrollers).

*Measures of psychomotor function and attention before and after treatment with study medication will be used to determine the extent to which the compound is associated with any adverse cognitive outcome. Two tests will be used to measure psychomotor function and attention; these are the CogState Detection (psychomotor function) and CogState Pediatric Identification (Go-No Go: attention) tasks.*

CogState Detection and CogState Pediatric Identification will assess task speed and accuracy, with faster task speeds and higher accuracy an indicator of a higher-level of cognition.

### **6.3. Other Endpoints**

#### **6.3.1. PK/PD Endpoints**

Not applicable.

### **6.4. Covariates**

- Not applicable.

#### **6.4.1. Exploratory Endpoint**

Not applicable.

## **7. HANDLING OF MISSING VALUES**

Missing data will be handled based on the nature of the endpoint and the proposed statistical methods for summarizing the data.

For all endpoints that include seizure rate, number of days with missing seizure diary data will be subtracted from the denominator of the 28-day seizure rate calculations. If seizure rate for a given subject and for any phase cannot be calculated due to missing information, the endpoint that involves seizure rate during that phase will be also missing.

For scales used in this study (eg, CBCL, C-SSRS), scores will be imputed according to the imputation rules and algorithms for missing component scores, that are provided in the data standard documents. Partial dates for AEs and concomitant medications will be imputed according to Pfizer standard algorithms.

## **8. STATISTICAL METHODOLOGY AND STATISTICAL ANALYSES**

All subject in this study will receive pregabalin, and all doses of pregabalin will be combined. *Data will be summarized into 3 groups defined by a combination of the subject's randomized treatment group in one of the previously participated studies (subjects previously on pregabalin will be combined across treatment groups) and the treatment received during this study. The 3 summary treatment groups will be described as:*

1. Pregabalin-Pregabalin: any dose of pregabalin from the previous study and pregabalin in this study.
2. Placebo-Pregabalin: placebo in the previous study and pregabalin in this study.
3. Direct Pregabalin: pregabalin only in this study and did not participate in any previous study.

*Additionally, all pregabalin data in this study will be combined “Overall”. Other than baseline, where relevant, information will be presented only for this study. Baseline values will be the last observation made prior to initiating double-blind dosing in Studies A0081041, A0081042, and A0081105. Subjects entering Study A0081106 directly will have baseline observations made at screening (Visit 1B).*

There will be 3 sets of analyses performed for most of safety endpoints where it is relevant. 1) Overall; 2) age cohorts); 3) primary seizure type. The three sets are described below.

1. Overall (all subjects in A0081106). This analysis is not applicable for seizure related endpoints due to nature of primary seizure type (PGTC, POS) and for some other safety endpoints where the assessment is not required for all subjects due to age differences.
2. Age cohorts: This *cohort analysis will consist of an age cohort defined as: 1 month to 16 years of age or age >=17*. For subjects from previous studies entering study A0081106, the age at randomization from their previous study will be used to determine the age cohort. For direct enrollers, age at screening/baseline of the present study will be used.
  - For some of vital signs and ECGs data where mean and standard deviation of the measurement are reported, the age cohorts will be (1 month to <2 years, 2 years to <4 years, 4 years to <10 years, 10 years to 16 years and >=17 years) and the “overall” summary and by seizure cohort summary will not be performed due to differences in normal range in younger age group.
3. *Primary seizure type cohorts are POS or PGTC seizures*). The partial onset seizure cohort consists of subjects from studies A0081041, A0081042, and A0081106 Direct Enrollers. The PGTC seizure cohort includes subjects from Study A0081105.

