#### **3.1. Treatments and Visits**

[figure not shown]
The day of the last visit (completion of taper phase) of Studies A0081041, A0081042, and A0081105 is designated as Day 1 (Visit 1A) of this study. Baseline values for analysis of change in safety endpoints will be the assessments made prior to initiating double-blind dosing at Visit 1 of Studies A0081041, A0081042, or A0081105. For subjects directly entering Study A0081106 without participation in one of the studies above, baseline values for analysis of change in safety endpoints will be the assessments made at the first visit (Screening Visit 1B) of this study.

For pediatric subjects, pregabalin dosing will initiate at the daily dose of 2.5 mg/kg/day (subjects  $\geq$ 30 kg) or 3.5 mg/kg/day (subjects  $<$ 30 kg) at this visit. Adult subjects who enroll in this study following participation in Study A0081105 will initiate dosing at 150 mg/day. All seizures experienced will be self-recorded by the subject or recorded by their parents/legally acceptable representative as appropriate, in a daily seizure diary beginning at Visit 1 and subsequently throughout the entire study.

Subjects will return for the designated assessments of safety, tolerability, and drug accountability at Week 1 (Visit 2), Month 1 (Visit 3), Month 2 (Visit 4), Month 4 (Visit 5), Month 6 (Visit 6), Month 9 (Visit 7), Month 12/Early Termination (Visit 8), and Follow-up (Visit 9). Investigator site staff will contact the subject and/or parent/caregiver by telephone at least monthly between visits, to address questions, assess safety and adverse events, and ensure compliance with study directives.

At Visit 2 and subsequent visits thereafter, the investigator or designee will review seizure diary data and tolerability with the subject and may adjust the dose at his/her discretion. For pediatric subjects with body weight  $\geq 30$  kg (1 month to 16 years of age), doses may remain the same or be adjusted upward in increments of no more than 2.5 mg/kg/day to daily dose levels of 5.0, 7.5, or 10.0 mg/kg/day. For pediatric subjects with body weight  $< 30$  kg, doses may be adjusted in increments of no more than 3.5 mg/kg/day to daily dose levels of 7.0, 10.5, or 14.0 mg/kg/day. For adult subjects (17 to 65 years of age) doses may be adjusted in increments of 150 mg/day to daily dose levels of 300, 450, or 600 mg/day.

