#### **7.6.3. Columbia-Suicide Severity Rating Scale (C-SSRS)- Subjects 6-65 Years of Age**

The C-SSRS is a prospective semi-structured interview comprised of the following areas of assessment: Ideation, Intensity of Ideation, Behavior and Lethality. It has been used extensively in global clinical studies (academic and industry sponsored) and in a range of therapeutic areas, disorders and indications, including psychiatry, neurology, obesity, urology and endocrinology and is FDA-approved. It has been translated into multiple languages.

The C-SSRS will be used to determine eligibility to enroll at Screening and at every follow-up visit to prospectively monitor suicidal ideation and behavior during the study. If a subject is unwilling or unable to respond, the parent or legally acceptable representative may answer any or all questions based upon their knowledge of the subject and observations of the subject's behavior. Subjects may be interviewed alone or with the parents or legally acceptable representative present based upon discretion of the interviewer.

The C-SSRS will be utilized for all subjects who are 6-65 years of age at Visit 1. The "Lifetime" version will be completed at Screening for those subjects who have not had it administered during participation to study A0081041 or at Visit 1B for direct enrolling subjects. The "Since Last Visit" version of the C-SSRS will be completed at Visits 1A, 2, 3, 4, 5, 6, 7, 8, and 9 or Early Termination. The "Since Last Visit" version will also be completed at any unscheduled clinic visits (ie, clinic visits not included in the [Schedule of Activities](#)). C-SSRS raters must demonstrate successful completion of required training and must have a valid rater training completion certificate in order to perform the assessment.

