### **8.3.9. Suicidal Ideation and Behavior**

#### C-CASA/C-SSRS

The denominator used in the percentages will be the number of subjects assessed for suicidal ideation and behavior (6 to 65 years of age).

The number and percent of subjects within each C-CASA category by treatment group and overall at baseline screening (lifetime) and at any time post-baseline without regard to baseline will be reported.

A subject listing of C-CASA categories as well as the underlying C-SSRS scale data will be presented.

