## Appendix 1. Data Derivation Details

This table describes how seizure related endpoints have been defined.	
Endpoint	Derivation
PGTC 28-day seizure rate at baseline: Baseline 28-day seizure rates will be observation made prior to initiating double-blind dosing in studies A0081105 during the 8 weeks baseline period)  There will not be baseline seizure rate for POS subject for reason described in Section 8 .	28-day seizure rate b = [(# of seizures b ) ÷ (#of days b - # of missing diary b )] × 28, where #of days b is defined as (first dose date-1) – screening date +1.
28-day seizure rate during treatment phase (excluding taper phase) POS, PGTC	28-day seizure rate t = [(# of seizures t ) ÷ (#of days t - # of missing diary t )] × 28, where #of days t is defined as date of last diary data entry for that visit – date of first diary data entry for that visit +1.
Seizure frequency for other type of seizure (ie, myoclonic, absence seizure, tonic/tonic, clonic, unclassified, status epilepticus) which are not part of 28-day seizure rate.	n (%) of subject experienced at least each other type of seizure will be calculated for POS population and PGTC population separately

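### Change from baseline for Placebo-Pregabalin, and in Overall where it is produced, includes the placebo period because no baseline at the start of pregabalin is defined

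*SAP*

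**What the plan says.** SAP section 8 states: "Baseline values will be the last observation made prior to initiating double-blind dosing in Studies A0081041, A0081042, and A0081105". The Statistical Methods part of the Protocol Summary and Protocol section 9 say the same. Direct enrollers take their baseline at Visit 1B. Apart from baseline, only A0081106 data are presented.

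SAP 2.1 words it differently. There the baseline values for change in safety endpoints "will be the assessments made prior to initiating double-blind dosing at Visit 1 of Studies A0081041, A0081042, or A0081105". Protocol 3.1 carries the same text and names the purpose: "Baseline values for analysis of change in safety endpoints will be the assessments made prior to initiating double-blind dosing at Visit 1" of the parent study.

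One of the three summary groups is "Placebo-Pregabalin: placebo in the previous study and pregabalin in this study". All three groups are also pooled into an Overall column, which SAP 8 describes as all the pregabalin data of the study.

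Day 1 of A0081106 (Visit 1A) is the last day of the parent study, after taper. Under Protocol 6.1 and footnote b of the Schedule of Activities, parent-study results stand in at Visit 1A for laboratory tests, vital signs, height, weight, Tanner stage, ECG, the suicidality scales and, for A0081041, CogState.

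**The concern.** The study exists to describe long-term safety on pregabalin, largely in children, and its endpoints include growth and development. Children gain height and weight, advance in Tanner stage and change on timed cognitive tasks simply as months pass.

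For Pregabalin-Pregabalin, the pre-double-blind value is the last one before pregabalin. For Direct Pregabalin, Visit 1B serves the same purpose. Only Placebo-Pregabalin has a stretch of study time without the drug between baseline and first pregabalin dose. That group's tables go from a pre-placebo value straight to visits on pregabalin, so whatever changed during placebo is inside the change score. In Overall the same subjects are merged with the rest and nothing marks the difference.

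This matters for interpretation. SAP 6.2.5 says that cognitive measures before and after study medication will be used to judge whether the compound is linked to an adverse cognitive outcome. For the placebo-treated A0081041 subjects, the SAP 8 baseline separates the before value from the first pregabalin dose by the whole placebo phase. Adverse events do not have this problem: SAP 6.2.1 counts them from the first day of A0081106 treatment.

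**Working it through.** The plan gives no figure on this point, so there is nothing to reproduce. The check has two parts.

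**1. Which baseline is the last value before pregabalin?**

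| Group | Baseline under SAP 8 | Last value before first pregabalin dose? |
|---|---|---|
| Pregabalin-Pregabalin | last value before parent double-blind dosing | yes |
| Placebo-Pregabalin | last value before parent double-blind dosing | no; the placebo period follows |
| Direct Pregabalin | Visit 1B | yes |

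The Visit 1 wording in SAP 2.1 and Protocol 3.1 gives the same pattern, because it too lies before double-blind dosing.

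**2. How much of the interval precedes pregabalin in Placebo-Pregabalin?**

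Inputs:
- Minimum double-blind time before entry from A0081041 or A0081105: 4 weeks = 28 days (Protocol 3 and 4.1).
- Full double-blind phase: 12 weeks = 84 days. This is an assumption. The current text does not state it, and only the Protocol's document history points to it.
- Double-blind length in A0081042: not given, so no share can be computed.
- Study days of the clinic visits: 60, 180, 270 and 365 (Schedule of Activities).

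Formula: share = P / (P + study day), where P is the number of days from baseline to first pregabalin dose.

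| Visit | Measured there | P = 28 | P = 84 (assumed) |
|---|---|---|---|
| Visit 4, Day 60 | vital signs | 28/88 = 31.8% | 84/144 = 58.3% |
| Visit 6, Day 180 | height, weight, laboratory, vital signs | 28/208 = 13.5% | 84/264 = 31.8% |
| Visit 7, Day 270 | vital signs | 28/298 = 9.4% | 84/354 = 23.7% |
| Visit 8, Day 365 | all of these, plus Tanner stage, ECG and CogState | 28/393 = 7.1% | 84/449 = 18.7% |

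If a 7-day parent-study taper is added (also an assumption), P = 91 and the Month 12 share is 91/456 = 20.0%.

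These are shares of time. They become shares of the change only if the measure moves linearly and the drug has no effect on it. As an illustration on those terms, with assumed growth of 2 to 3 kg a year, the weight gain dated before pregabalin runs from 2 × 28/365 = 0.15 kg to 3 × 84/365 = 0.69 kg.

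With the last value before the first A0081106 dose as baseline, P is about 0 and the share is about 0% at every visit.

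**The case against.** The best case for the plan is that a common pre-double-blind baseline was prespecified, is worded alike in three places, and treats all roll-over subjects the same way. The group is named for its history and has its own column. Nothing is tested, and no text labels the result as change on pregabalin. Replacing the baseline would give Placebo-Pregabalin a reference taken after a placebo period. This stands as a reason to keep the prespecified table, but not as a reason to have it alone.

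The scope is also narrower than it may seem. Only Placebo-Pregabalin and Overall are touched. POS seizure rates have no baseline, and PGTC rates are given by visit with no change score specified (SAP 8.3.6). Where vital signs and ECG are shown as mean and standard deviation by narrow age bands, SAP 8 makes no Overall summary. CogState has a separate analysis plan, and laboratory, height and weight tables follow sponsor standards. Neither is available, so either could already deal with this.

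Two stronger readings are tempting.
- A reader might infer that SAP 2.1 and SAP 8 yield different values, up to 8 weeks apart in A0081105, since SAP Appendix 1 places seizure counts "during the 8 weeks baseline period". The SAP 2.1 text can equally mean that dosing began at Visit 1, and the parent visit schedules are not in the documents. A difference is possible but not shown.
- A reader might infer that placebo-phase suicidality is counted against pregabalin. Protocol 7.6.3 says the Since Last Visit "version of the C-SSRS will be completed at Visits 1A, 2, 3, 4, 5, 6, 7, 8, and 9", and SAP 8.3.9 says that categories "at any time post-baseline without regard to baseline will be reported". But Protocol 6.1 treats the Visit 1A result as parent-study data, and SAP 8 presents only A0081106 data apart from baseline. Read together, these keep the Visit 1A result out of the post-baseline count. A clarifying sentence is enough.

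**Conclusion.** The point holds for change-from-baseline summaries in Placebo-Pregabalin, and in Overall where that column is produced. For subjects from A0081041 and A0081105, the off-drug part of the interval is 7.1% to 18.7% at Month 12 and 13.5% to 31.8% at Month 6. The lower ends rest on the stated 4-week minimum and the upper ends on an assumed 12-week phase. For A0081042 the size is unknown.

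This is a fault of interpretation in descriptive tables and invalidates no test. It is worth correcting because growth and cognition are among the affected endpoints, and because most of the values needed are already collected. The endocrine panel may be an exception: Protocol 7.3.3 lists it for Visits 1B and 8 only, so a last-visit value from the parent study is not assured.

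**What to change.** 1. In SAP 8, define a second baseline for Placebo-Pregabalin: the last observation before the first A0081106 dose (parent-study last visit, Visit 1A), where it exists. Report this group's change from it. Where Overall is produced, let Placebo-Pregabalin subjects enter with this value. The other two groups already start from their last pre-pregabalin value.
2. Keep the tables on the prespecified pre-double-blind baseline alongside, so that the common reference for roll-over subjects is not lost.
3. As clarifications only, use one baseline wording in SAP 2.1 and SAP 8, and state in SAP 8.3.9 that post-baseline for the C-SSRS and CBCL means after the first A0081106 dose.
4. Ask for the separate CogState analysis plan to use the same definition.

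The cost is SAP wording, one baseline flag and one extra set of tables, with no new data collection. The drawback is that the Placebo-Pregabalin reference becomes a post-placebo value, which is why both sets should be shown.
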